#### 4.1.2. Phase II:

The Phase II portion will open after determination of the RP2D of the combination of telaglenastat and AZA from the Phase 1b portion. The RP2D will be selected based on the totality of the clinical data (safety, tolerability, PK, PDn, and efficacy) and will not exceed the MTD. A total of 28 evaluable MDS patients, which includes 22 Phase II patients and 6 patients treated at the RP2D from Phase 1, will be enrolled. We will enroll 16 patients in the first stage. If 6 or fewer patients achieve response, enrollment will be halted. If 7 or more out of the first 16 patients achieve response, accrual will continue until a total of 28 patients have been enrolled. If 15 or more out of these 28 patients achieve response, the treatment will be considered efficacious and worthy of further investigation. Toxicities will be monitored closely using the method of Thall et al (1995) in Section 8.1.3.

### 4.2. Study Duration:

- 4.2.1. All subjects must complete a screening visit, day 1 visits for each new cycle, and an end-of-treatment visit.
- 4.2.2. Treatment will continue until discontinuation due to relapse, unacceptable toxicity, or disease progression as defined by the IWG 2006 criteria for MDS. This includes:
  - clinically significant progressive disease at any time, or

NCT ID: NCT03047993

Protocol 2016-0636 ate: 06/03/2019

Page **15** of **39** 

- a lack of clinical benefit after 5 cycles of treatment at the highest dose of study medication, or
- Possibility of undergoing allogeneic stem cell transplantation
- discontinuation of study drug for more than 6 weeks, or
- intercurrent illness that prevents further administration of treatment, or
- unacceptable adverse event(s), or
- patient decision for study withdrawal, or
- general or specific changes in the patient's condition that render the patient unacceptable for further treatment in the judgment of the investigator

Patients may remain on study for up to 12 cycles if the patient demonstrates clinical benefit and no excessive toxicity (i.e. no clinically significant study-drug related grade  $\geq$  3 toxicity). Patients who are experiencing clinical benefit and have not experienced excessive toxicity may be eligible to continue therapy after discussion with the PI and the discussion documented in the patient's medical record.

If one of the study agents is discontinued due to toxicity, the patient may remain on study until the occurrence of significant disease progression, severe toxicity that requires all study agents to be permanently discontinued, or at the discretion of the PI.

# 4.2.3. Cycle Length:

Study cycles will be administered every 28 days + 5 days or upon resolution of any clinically significant study drug related AE to grade 0-2, whichever occurs first.

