#### 4. TREATMENT PLAN

# 4.1 Study Design

NCT ID: NCT03047993 Protocol 2016-0636 ate: 06/03/2019

Page **13** of **39** 

This is a Phase 1b/II clinical trial designed to assess the safety, tolerability and efficacy of telaglenastat in combination with AZA for the treatment of advanced MDS. Patients will be treated with standard AZA (IV or SQ 75mg/m2 IV daily x 7 days) and telaglenastat orally twice daily continuously for 28 days per treatment cycle. A cycle will consist of 28 days of dosing. Patients will continue on study therapy unless they have evidence of progressive disease or unacceptable toxicity. Other objectives include exploring the PK and PDn of telaglenastat in combination with AZA.

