# 4.5 Dosing Delays and Dose Modifications:

## 4.5.1. Dose Adjustments:

The doses of telaglenastat and AZA will be adjusted according to the guidelines shown in the following tables for study drug-related clinically significant toxicity. If toxicity is not covered in the table, doses may be reduced or held at the discretion of the investigator for the patient's safety.

Patients will be withdrawn from the study if they fail to recover to CTCAE v4.03 grade 0 to 1 (or within 1 grade of starting values for pre-existing laboratory abnormalities) from a clinically significant non-hematologic treatment-related toxicity within 6 weeks (leading to treatment delay of > 4 weeks) unless the investigator feels that the patient should remain in the study because of evidence that the patient is/may continue deriving benefit from continuing study treatment. Such instances will be discussed with the principal investigator on a case by case basis and the discussion documented in the medical record.

Protocol 2016-0636 Date: 06/03/2019

Page **18** of **39** 

Patients with study-drug related toxicities that are manageable with supportive therapy may not require dose reductions. For patients with other drug-related toxicities, the following dose adjustment rules apply:

	NCI CTCAE v4.03 Grade	Action
	Grade 0-2 non-hematological toxicity	No dose reduction.  For grade 2 toxicities that are persistent and/or intolerable (e.g. stomatitis) patients may
		have a treatment interruption or dose reductions to the next lower dose level.
4.5.2.	Grade 3-4 clinically significant non-hematological toxicity†	Hold until recover to NCI CTC AE grade 0-1
		If recovery occurs within 4 weeks after treatment has been held, dose should be reduced to -1 dose level, if applicable.

Administration of subsequent cycles should be administered when neutrophils recover to  $\geq 1 \times 10^{9}$ /L and platelets to  $\geq 30 \times 10^{9}$ /L, or to baseline levels prior to the start of the last cycle of therapy. Patients with residual disease may start the next cycle with neutrophil and/or platelet counts lower than these if judged to be in the best interest of the patient. The decision to treat should be documented in the patient's medical record.

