#### 5.2.3. Cycle 1 Day 8, Day 15, Day 22 (+/- 3 days)

At these Cycle 1 mid-cycle assessments, patients will return to clinic to undergo the following procedures:

NCT ID: NCT03047993

Protocol 2016-0636 ate: 06/03/2019 Version 1

Page **21** of **39** 

- 1. AE monitoring
- 2. Recording of concomitant medications
- 3. Vital signs and weight
- 4. Symptom-directed physical exam
- 5. Clinical laboratory evaluation (hematology, serum chemistries)
- 6. Plasma samples for PK analysis pre-dose on C1D15
- \*Patients may take their telaglenastat doses prior to, during, or after their clinic visit according to their usual dosing schedule because there are no specified pre-dose procedures *with the exception of C1D15* where the patient should not take their telaglenastat dose prior to arrival due to pre-dose PK sample.

## 5.2.4. Cycle 2 Day 1 (+/- 5 days) and all subsequent cycles on Day 1

Patients may take their telaglenastat doses prior to, during, or after their clinic visit according to their usual dosing schedule because there are no specified pre-dose study procedures *with the exception of C2D1 and C3D1* due to pre-dose PK samples.

- 1. Vital signs and weight
- 2. AE monitoring
- 3. Recording of concomitant medications
- 4. Symptom-directed physical exam
- 5. Clinical laboratory values (hematology, serum chemistry)
- 6. Plasma sample for exploratory biomarker analysis
- 7. Bone marrow evaluation of tumor/disease burden is required for all patients receiving telaglenastat on cycle 2 day 1, cycle 4 day 1, cycle 6 day 1, and every 3 cycles thereafter, +/- 5 days for all above assessments. Additional evaluations are acceptable as clinically indicated.
- 8. Bone marrow sample for biomarker and pharmacodynamics analysis during above protocol-defined time points.
- 9. Plasma samples for correlative analysis on same day as bone marrow sample timepoints are collected
- 10. Plasma samples for PK analysis prior to the administration of study drug, on C2D1 and C3D1.

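### Section 4.2.3 starts each cycle at the earlier of the calendar date or adverse-event recovery, so its recovery condition can never delay dosing, and it conflicts with the Section 4.5 hold to grade 0-1

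*Combined protocol and SAP*

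**What the plan says.** Section 4.2.3 (Cycle Length) gives two triggers for the next cycle. One is the calendar, 28 days with a window of 5 days either side. The other is recovery: "upon resolution of any clinically significant study drug related AE to grade 0-2, whichever occurs first". Section 4.1 adds: "A cycle will consist of 28 days of dosing".

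Section 4.5 (Dosing Delays and Dose Modifications) has its own rules for study-drug-related toxicity:

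- For "Grade 3-4 clinically significant non-hematological toxicity", the table says "Hold until recover to NCI CTC AE grade 0-1", and then "If recovery occurs within 4 weeks after treatment has been held, dose should be reduced to -1 dose level, if applicable".
- For grade 0-2 non-hematological toxicity, no dose reduction is required. Interruption or reduction is optional for persistent or intolerable grade 2 events.
- Section 4.5.1 withdraws patients who "fail to recover to CTCAE v4.03 grade 0 to 1 (or within 1 grade of starting values for pre-existing laboratory abnormalities") from a clinically significant related non-hematological toxicity within 6 weeks. The investigator may make an exception for a patient who is benefiting.
- A separate sentence covers blood counts: "Administration of subsequent cycles should be administered when neutrophils recover to" a stated level, with a matching platelet condition.

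The visit schedule in Section 5.2.4, headed "Cycle 2 Day 1 (+/- 5 days) and all subsequent cycles on Day 1", requires adverse-event monitoring but names no grade at which a cycle may start.

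**The concern.** A recovery condition in a cycle-start rule is there to postpone dosing until the patient is fit for it. Joined to the calendar by the earlier of the two, it does not do that. Section 4.2.3 also uses a looser recovery grade (0-2) than the Section 4.5 hold (0-1). The two sections can therefore give opposite instructions for the same patient on the same day.

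What is at stake is a dosing instruction. Followed literally, 4.2.3 begins another cycle in a patient whom 4.5 keeps off treatment. The sentence in 4.5 that speaks directly about starting later cycles covers only neutrophils and platelets. For non-hematological events, 4.2.3 is the sentence that names a recovery grade in a rule about when a cycle begins. Section 4.2.4.1 also lets local physicians and regional care centers give azacitidine, so clinicians outside the main site may need to apply the rule. The letter to those physicians is not among the documents, so it is unknown whether it settles the matter.

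**Working it through.** This is a check of logic. It involves no sample size or error rate, and the plan gives no figure to reproduce.

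**Inputs.** Let C be the calendar date, counted in days from the start of the current cycle: nominally 28, allowed from 28 − 5 = 23 to 28 + 5 = 33 (Section 4.2.3). Let R be the day on which the related event resolves to grade 0-2 (Section 4.2.3).

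**Rule as written.** Start = min(C, R). Because min(C, R) ≤ C for every R, the recovery condition cannot move a start past the calendar window. With C = 28:

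- R = 31 gives a start on day 28, before recovery.
- R = 45 gives a start on day 28, or day 33 at the latest, with the event unresolved.

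**Rule that would delay dosing.** Start = max(C, R). With C = 28, R = 20 gives day 28, R = 31 gives day 31, and R = 45 gives day 45.

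**The two sections side by side** (related, clinically significant, non-hematological event):

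| Patient's state | Section 4.2.3 | Section 4.5 table | Conflict |
|---|---|---|---|
| Grade 3, unresolved at day 33 | Cycle due | Hold | Yes, on timing |
| Was grade 3, now grade 2 at day 28 | Cycle due | Hold, grade 0-1 not reached | Yes, on grade |
| Was grade 3, now grade 1 at day 28 | Cycle due | Restart at dose level -1, if recovery came within 4 weeks of the hold | No, on start date |
| Never above grade 2 | Cycle due | No dose reduction required, interruption optional | No |

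**Would changing one word be enough?** No. Replacing the earlier date with the later one resolves the first row while the event stays at grade 3. The second row remains, because grade 2 satisfies 4.2.3 and not the hold. The recovery grade has to follow Section 4.5 as well.

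**The case against.** The strongest reply is that Section 4.5 already covers this. It is the section on delays and modifications, it sets count-recovery conditions for later cycles, and 4.2.3 is headed only as a rule on cycle length. A careful reader would treat 4.5 as the specific rule and follow it. That is probably what sites would do, and it keeps the point minor. But no visible text says so.

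Four further points narrow it, and they stand:

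- Section 4.5.1 says that toxicities manageable with supportive care may not need a dose reduction, and it applies its table to other drug-related toxicities. Some grade 3 events may therefore fall outside the hold.
- The hold row carries a dagger whose footnote is not shown. It could define, exempt or cross-refer.
- Section 4.2.2 ties staying on study for up to 12 cycles to clinical benefit without clinically significant related grade 3 or higher toxicity. This works against automatic re-treatment by the calendar.
- Other safeguards exist: adverse-event monitoring on day 1 of each cycle, discontinuation for unacceptable events, serious adverse event reporting, and toxicity summaries every 7 evaluable patients. None of these states the grade that permits the next cycle.

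A reader might infer three stronger things, which the documents do not support:

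- *That no cycle can be delayed for toxicity.* Section 4.5 can delay one, through the hold and through the count rule. Only the recovery condition inside 4.2.3 is inert.
- *That a cycle could start early.* With R = 20 the literal formula gives day 20, before the window opens at day 23, but Section 4.1 fixes a cycle at 28 days of dosing.
- *That the 4-week figure in the table caps how long the two rules disagree.* It only conditions the restart at dose level -1. Withdrawal comes at 6 weeks, with no stated starting point for that count, and the investigator exception has no end date.

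**Conclusion.** Section 4.2.3 is wrong as written. Its recovery condition has no delaying effect, and for related, clinically significant grade 3-4 non-hematological toxicity it disagrees with Section 4.5 on both timing and grade. The word chosen looks like a slip for its opposite. This is a minor inconsistency in safety wording.

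How often it would matter cannot be estimated. Section 2.7 describes non-hematological events in 11 leukemia patients on twice-daily monotherapy as typically grade 1/2, though it lists one related grade 3/4 hyponatremia and one stomatitis. Those data do not include azacitidine toxicity. The number of affected patients may be small.

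The 16-patient first stage, the 15-of-28 response decision and the toxicity stopping boundaries do not depend on this sentence.

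Confidence is moderate. The conclusion rests on the literal text of 4.2.3 and on the unseen footnote not already resolving the conflict. A reader with the full table should check that footnote first.

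**What to change.** Reword Section 4.2.3 along these lines:

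*Each new cycle starts 28 days ± 5 days after the start of the previous one, or upon recovery from any clinically significant study-drug-related AE as required by Section 4.5, whichever occurs later. If the two sections differ, the hold, dose-reduction, blood-count recovery and investigator-exception rules of Section 4.5 govern.*

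This points to Section 4.5 for the recovery grade instead of restating one. It therefore keeps the supportive-care provision and the benefit exception intact. It also avoids carrying the allowance for pre-existing laboratory abnormalities, which belongs to the withdrawal rule, into the restart rule. All thresholds and time limits in Section 4.5 stay as they are.

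The cost is a short rewording of one section in the next amendment. It adds no visits, tests or patients.

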## 4.2.4. Cycle Administration:

- 4.2.4.1. AZA may be administered by MDACC or local physician, inclusive of the regional care centers. Commercial supplies and institutional standards for administration of AZA will be used and records will be obtained from the local physician as indicated in the Dear Doctor Letter. Institutional standards include administration of AZA on the "5-2-2" schedule.
- 4.2.4.2. Telaglenastat should be taken orally twice daily with food. The first telaglenastat dose of the day will be administered immediately after breakfast. The evening/second dose should be taken with a meal approximately 12 hours (+/- 2 hours) after the morning dose.

NCT ID: NCT03047993

Protocol 2016-0636 ate: 06/03/2019

Page **16** of **39** 

- 4.2.4.3. Telaglenastat will be self-administered primarily on an outpatient basis; but may be administered as an inpatient.
- 4.2.4.4. Patient compliance will be documented using the MDACC Research Medication Diary and will be assessed at each study visit.
- 4.2.4.5. Missed doses should be skipped. If a patient forgets to take a dose of study drug and they are outside the allotted protocol window (+/- 6 hours) they should be instructed NOT to take extra study drug at their next administration. If a dose is delayed by <6 hours, they should be instructed to take the dose and then to take the next dose at the normal time.

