#### 4.1.1. Phase 1b:

In the Phase 1b portion, telaglenastat will be administered at the goal starting dose level 0 of 600mg BID continuously. The MTD is defined as the highest dose level with </= 1 out of 6 patients experiencing a DLT during the first cycle.

The first 6 patients will be treated at dose level 0. If </= 1 out of the 6 patients experience a DLT during the first cycle, this level will be identified as the RP2D and the study will progress to the Phase II portion. If > 2 out of the 6 patients experience a DLT during the first cycle, this dose level would exceed the MTD, and an additional 6 patients will be treated at the next lower dose level. Reduced dose level -1 is defined in Table 1 below. Patients treated in the Phase 1b portion that are removed from study before day 28 for any reason other than toxicity, and have not experienced DLT, will be replaced.

AZA will be administered subcutaneously (SQ) or intravenously (IV) for 7 days of every cycle (days 1-7) as determined by the treating physician. Both SQ and IV forms of administration are FDA-approved and are considered interchangeable, based on patient and physician preference.

Table 1: Dose de-escalation for telaglenastat and AZA

Dose Level	CB-839 (oral)	AZA (IV or SQ)
0	600 mg BID days 1-28	75 mg/m2 days 1-7
-1	400 mg BID days 1-28	75 mg/m2 days 1-7

Dose reductions beyond those mentioned in this table or different to the doses specified should be discussed with the PI and documentation of the justification recorded in the medical record.

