#### 4.1.1.2. Dose De-escalation Procedures:

A dose-limiting toxicity (DLT) is defined as any Grade 3 or higher non-hematologic adverse event or abnormal laboratory value occurring during the first cycle (i.e. the first 28 days) on study except those that are clearly and incontrovertibly due to disease progression or extraneous causes, with the following exceptions:

Protocol 2016-0636 ate: 06/03/2019

Page **14** of **39** 

 CTCAE v4.03 Grade 3 AST or ALT that resolves to < Grade 2 within 14 days
 without an associated rise in bilirubin

- Grade 3 nausea, vomiting or diarrhea that can be managed to < Grade 2 with
 standard antiemetic or antidiarrheal medications
- Grade > 3 electrolyte abnormality that lasts < 24 to 72 hours, is not clinically complicated, and resolves spontaneously or responds to conventional medical interventions
- Grade 3 biochemical abnormalities of amylase or lipase without clinical evidence of pancreatitis

Hematologic DLT is defined as Grade > 3 neutropenia and/or thrombocytopenia with a hypocellular bone marrow lasting for 6 weeks or more after the start of a course in the absence of underlying MDS. Anemia will not be considered for the definition of DLT.

**4.1.1.3**. The first 6 patients will be treated at dose level 0. If DLT occurs in > 2/6 evaluable patients, this dose level would exceed the MTD, and an additional 6 patients will be treated at the lower dose level. The highest dose level at which 0-1/6 patients experience DLT will be used as the RP2D. Should >2/6 DLTs occur in dose level -1, the combination may be considered too toxic in this indication and the study may be discontinued.

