# 5.2.2. Cycle 1 Days 2-7:

During Cycle 1 and all subsequent cycles, Days 2-7, patient will undergo vital signs prior to azacitidine administration. Patients may take their telaglenastat doses prior to, during, or after their AZA according to their usual dosing schedule.

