#### 8.2.2. DLT-evaluable:

Unless doses are missed in Cycle 1 due to DLT(s), a patient must receive at least 85% of the planned doses of telaglenastat and at least  $\geq$  5 doses of azacitidine to be considered evaluable for DLTs. If a patient received fewer doses of telaglenastat or AZA in the first 28 days of treatment for reasons other than a DLT, the patient will be considered non-evaluable for DLT and replaced.

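### The protocol fixes azacitidine to days 1-7 in the dose-level table and the vital-signs rule, but also allows an undefined 5-2-2 schedule that neither covers

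*Combined protocol and SAP*

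**What the plan says.** Four places state when azacitidine is given, or what is done on the days it is given.

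- Section 4.1 (Study Design): "Patients will be treated with standard AZA (IV or SQ 75mg/m2 IV daily x 7 days".
- Section 4.1.1 (Phase 1b), text: "AZA will be administered subcutaneously (SQ) or intravenously (IV) for 7 days of every cycle (days 1-7) as determined by the treating physician". The dose-level table in the same section has the entry "75 mg/m2 days 1-7" at level 0 and again at level -1.
- Section 5.2.2: "During Cycle 1 and all subsequent cycles, Days 2-7, patient will undergo vital signs prior to azacitidine administration".
- Section 4.2.4.1 (Cycle Administration): "Commercial supplies and institutional standards for administration of AZA will be used", followed by "Institutional standards include administration of AZA on the '5-2-2' schedule".

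The last provision applies to azacitidine given at the study institution, at its regional care centers or by a local physician. The documents do not define 5-2-2. They do not confine it to Phase II or to later cycles, and they do not list it in the dose-level table.

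**The concern.** The dose-level table defines the combination regimen under test, and Section 5.2.2 defines what is checked before azacitidine is given. If a schedule is permitted elsewhere but appears in neither place, two practical problems follow.

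First, compliance is ambiguous. The same cycle can be correct under Section 4.2.4.1 and a departure from Section 4.1.1, and a monitor could not tell from the protocol whether to log a deviation.

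Secondly, a procedure tied to calendar days does not follow the drug when dosing moves to other days. Staff who apply Section 5.2.2 as written would have no instruction to take vital signs before a dose given after day 7.

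**Working it through.** No stated figure is at stake, so the check is a comparison of the passages and a day count.

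**Inputs.** 75 mg/m2 per dose and days 1-7 (Section 4.1.1 and its table); vital signs on Days 2-7 of all cycles (Section 5.2.2); 5-2-2 permitted (Section 4.2.4.1); Cycle 1 visits on Days 8, 15 and 22, each +/- 3 days (Section 5.2.3); a response window of 6 cycles (Section 8.1.2).

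**Assumption.** 5-2-2 means five days on, two off, two on: days 1-5 and days 8-9.

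**Day count**

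| | Days 1-7 | 5-2-2 (assumed) |
|---|---|---|
| Doses per cycle | 7 | 5 + 2 = 7 |
| Total per cycle | 7 x 75 = 525 mg/m2 | 7 x 75 = 525 mg/m2 |
| Days found in this schedule only | 6, 7 | 8, 9 |
| Doses after day 7 | 0 | 2 of 7 = 28.6% |

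The two schedules differ in timing, not in the number of doses or the total.

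**Coverage of vital signs.** Day 1 has its own visit with vital signs in every cycle, and Section 5.2.2 covers Days 2-7. For days 8 and 9:

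- Cycle 1: the Day 8 visit includes vital signs, but Section 5.2.3 does not say that they precede azacitidine, and the visit may fall anywhere from day 5 to day 11.
- Cycle 2 onward: Section 5.2.4 schedules Day 1 visits only, so no visit covers days 8-9.

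The gap is therefore up to 2 doses per cycle. The ceiling over the response window is 6 x 2 = 12 of 6 x 7 = 42 doses, for a patient on 5-2-2 in all six cycles. It is 11 of 42 if the Cycle 1 Day 8 vital signs happen to precede a dose.

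**What does not move**

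- DLT rule: Section 4.1.1.3 says "The highest dose level at which 0-1/6 patients experience DLT will be used as the RP2D". Both levels carry the same azacitidine entry and differ only in telaglenastat.
- DLT evaluability: Section 8.2.2 requires at least 5 "doses of azacitidine to be considered evaluable for DLTs". This is a count of doses, and either schedule can meet it.
- DLT window: under 5-2-2 the last dose is on day 9, which leaves 28 - 9 = 19 days of cycle 1, against 28 - 7 = 21 days.
- Simon design (stop at 6 or fewer of 16; success at 15 or more of 28): exact binomial calculation gives type I error 0.099, power 0.803, early-termination probability 0.527 and expected sample size 21.7. These agree with the stated 10%, 80%, 53% and 22.
- Toxicity boundaries of 4/7, 7/14 and 10/21, and the operating characteristics in the Section 8.1.3 table, also reproduce. None of these calculations uses the azacitidine schedule.

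**The case against.** The strongest reply is that Section 4.2.4.1 is an express provision. A patient on 5-2-2 is treated as the protocol permits, receives the same number of doses on the assumed reading, and is covered by institutional standards for giving azacitidine. On this view the days 1-7 wording is shorthand and nothing is wrong beyond drafting.

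Much of that stands. The allowance looks deliberate, and the difference is one of timing. It does not remove the mismatch, because the allowance was not carried into the dose-level table or Section 5.2.2. Section 4.1.1 calls the SQ and IV routes interchangeable but says nothing similar about schedules. Its reference to the treating physician's choice leads into a statement about route.

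A reader might infer three stronger things, which the documents do not support.

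- **That the RP2D decision is compromised, because it is set on one regimen and applied to another.** The allowance is not limited by phase, so it reaches the six Phase 1b patients as well as those in Phase II. A split between the phases is possible but not built in, and azacitidine schedule is not what the dose levels vary.
- **That there is no record of the schedule given.** Section 4.2.4.1 provides for records from the local physician, and Section 7.5 lists pharmacy and hospital records among the source documents. The supportable statement is narrower: the text does not require the dosing days to be captured as a data item or summarised.
- **That the Day 8 visit is meant to follow azacitidine and would be displaced by 5-2-2.** Section 5.2.3 calls it a mid-cycle assessment and does not tie it to the end of azacitidine. With its window it can fall on day 5 or 6, before the last dose, under days 1-7 as well.

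**Conclusion.** The inconsistency is real and minor. Sections 4.1, 4.1.1 (with its table) and 5.2.2 describe azacitidine on days 1-7, while Section 4.2.4.1 permits a schedule that none of them accommodates. On the assumed meaning of 5-2-2, 2 of 7 doses per cycle lie outside the dose-level table, and up to two per cycle have no protocol-required pre-dose vital signs. How many patients would be affected cannot be judged from the documents, which do not say how often 5-2-2 would be used.

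The conclusion that the passages disagree depends on the assumed definition only in that some dose must fall after day 7. The exact count of two depends on it fully. The finding has no bearing on sample size, error rates, stopping boundaries or the DLT rule.

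**What to change.** 1. Reconcile Sections 4.1, 4.1.1 (including its dose-level table), 4.2.4.1 and 5.2.2, so that the azacitidine schedule or schedules covered by each dose level are stated in the same way everywhere. Define 5-2-2 if it is kept, and state whether the allowance applies in cycle 1 of Phase 1b. Which schedule is right is for the sponsor and investigator to decide.
2. In Section 5.2.2, tie the vital signs to each azacitidine administration day rather than to Days 2-7.
3. Capture the actual azacitidine dosing days on the CRF for each cycle.

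The cost is amendment wording and one CRF item. Tabulating cycle-1 DLTs by schedule is optional. With 6 patients in Phase 1b at the RP2D and 28 in all, the subgroups would be too small to guide a decision.
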